Protocol Title:	Optical Coherence Tomography Predictors of Functionally Significant Side Branch Compromise after Provisional Main Vessel Stenting In Bifurcation Lesions Assessed by Fractional Flow Reserve (ORBID – FFR)
Principal Investigator Name/Contact Info:	[name]./ [name]/ [contact]
Primary Contact Name/Contact Info	[name] /[name] / [contact] [name] /[name] [contact]
Date Revised:	January 19, 2017
Study Number:	HSM# 16-00041/ GCO#1: 16-0204(0001)

informed consent document, a copy will be placed in the subject's chart and the original copy will be stored in a secure location in the research office.

b) Inclusion and Exclusion Criteria

1. General inclusion criteria. Subjects will be enrolled in the study, if **ALL** of the following criteria are met

- All patients over 18 years of age presenting with stable coronary artery disease.
- Patients must have a clinical indication for coronary intervention.
- Creatinine Kinase Myocardial-Band Isoenzyme (CK-MB) must be less than or equal to the upper limit of lab normal (ULN) value within eight hours prior to the procedure

2. Angiographic inclusion criteria. Subjects will be enrolled in the study, if **ALL** of the following criteria are met:

- The target lesion must be a *de novo* calcified bifurcation coronary lesion that hasn't been previously treated with any interventional procedure for which provisional main vessel stenting strategy is planned after reviewing angiogram.
- The target vessel must be a native coronary artery with
 - a) stenosis $\geq 70\%$ and $<100\%$, or
 - b) Stenosis $\geq 50\%$ and $<70\%$ with evidence of clinical ischemia via positive stress test, or FFR ≤ 0.8 , or IVUS or OCT minimal lumen area $\leq 4.0 \text{ mm}^2$.
- The target lesion should have SB DS 30 - 70%.
- The target main vessel reference diameter must be $\geq 2.5 \text{ mm}$ and $\leq 4.0 \text{ mm}$.
- The SB reference diameter must be $> 2 \text{ mm}$ by coronary angiogram.
- The target vessel must have a Thrombolysis in Myocardial Infarction (TIMI) flow grade 3 at baseline.

Protocol Title:	Optical Coherence Tomography Predictors of Functionally Significant Side Branch Compromise after Provisional Main Vessel Stenting In Bifurcation Lesions Assessed by Fractional Flow Reserve (ORBID – FFR)
Principal Investigator Name/Contact Info:	[name]./ [name]/ [contact]
Primary Contact Name/Contact Info	[name] /[name] / [contact] [name] /[name] [contact]

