Date Revised:	January 19, 2017
Study Number:	HSM# 16-00041/ GCO#1: 16-0204(0001)

General exclusion criteria: Patient will not be enrolled in the study if ANY of the following criteria are present in the patient.

- Patients with ostial left main artery lesions or ostial right coronary artery lesions
- Female patients with child bearing potential not taking adequate contraceptives or currently breastfeeding
- Known allergy to acetylsalicylic acid or clopidogrel.
- Planned surgery within 12 months.
- History of bleeding diathesis
- Major surgery within 15 days
- Life expectancy < 12 months.
- Patients with kidney dysfunction (CrCl<30)

c) Number of Subjects

One hundred and fifty (150) consecutive patients with lesions requiring PCI of main vessel with drug eluting stent implantation for the treatment of stable CAD will be included in the study.

d) Study Timelines

This is a randomized study with one visit and no clinical follow-ups.

e) Study Endpoints

The primary endpoint is SB compromise defined as SB DS \geq 70%, or dissection or TIMI < 3.

The secondary endpoints

- SB FFR after main vessel stenting and its correlation with OCT imaging parameters before PCI
- OCT predictors of SB TIMI flow reduction after main vessel PCI
- Off-line analysis of SB stenosis by 3D-OCT and its correlation with FFR; correlation between 3D-QCA measurements, 3D-OCT, and FFR data.

Protocol Title:	Optical Coherence Tomography Predictors of Functionally Significant Side Branch Compromise after Provisional Main Vessel Stenting In Bifurcation Lesions Assessed by Fractional Flow Reserve (ORBID – FFR)
Principal Investigator Name/Contact Info:	[name]./ [name]/ [contact]
Primary Contact Name/Contact Info	[name] /[name] / [contact] [name] /[name] [contact]
Date Revised:	January 19, 2017
Study Number:	HSM# 16-00041/ GCO#1: 16-0204(0001)

- Association between calcification assessment by angiography and OCT imaging.
- FFR Device Success (ability to successfully deliver FFR wire to desired SB distal segment [n/150]).
- FFR Wire Workhorse Capability (proportion of patients [n/150] in which FFR wire able to serve as rail to deliver additional interventional devices to target SB lesion).

f) Procedures Involved in the Human Research

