Stable CAD patients with bifurcation lesions in whom provisional stenting strategy is planned, who have moderate or severe calcification in the main vessel lesion identified by angiography, SB stenosis 30-70% and SB reference diameter > 2mm will be enrolled in the study.

Moderate calcification will be defined as radiopaque density observed only during the cardiac cycle and typically involving only one side of the vascular wall, and severe calcification will be defined as radiopaque density noted without cardiac motion prior to contrast injection and involving both sides of the arterial wall. After completion of diagnostic angiogram and confirmation of subject eligibility, subjects will be randomly assigned to Rotational atherectomy (RA or Cutting Balloon Angioplasty (CBA)/PTCA group in a 1:1 fashion.

Patients in both groups will undergo PCI with stent implantation according to current standards of care. Lesion preparation including lesion pre-dilation, scoring or sculpting balloon angioplasty, and use of atherectomy and protection devices will be performed at the operator's discretion, followed by MV stenting. The operator will also decide in both groups about the length and size of the implanted stent. Procedural optimization, such as post-dilation or additional stent implantation will be performed based only on the angiographic findings, according to the discretion of the operator.

Protocol Title:	Optical Coherence Tomography Predictors of Functionally Significant Side Branch Compromise after Provisional Main Vessel Stenting In Bifurcation Lesions Assessed by Fractional Flow Reserve (ORBID – FFR)
Principal Investigator Name/Contact Info:	[name]./ [name]/ [contact]
Primary Contact Name/Contact Info	[name] /[name] / [contact] [name] /[name] [contact]
Date Revised:	January 19, 2017
Study Number:	HSM# 16-00041/ GCO#1: 16-0204(0001)

Optical coherence tomography (OCT) is an established medical imaging technique that uses light to capture micrometer-resolution, three-dimensional images from within optical scattering media will be performed to analyze plaque morphology, the extent and location of calcification, side branch size, angle, and ostial involvement.

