Patients in both groups will undergo (standard of care) a percutaneous coronary intervention (PCI), also known as coronary angioplasty, is a nonsurgical technique for treating obstructive coronary artery disease, including unstable angina, acute myocardial infarction (MI), and multivessel coronary artery disease (CAD) with stent implantation according to current standards of care. Lesion preparation including lesion pre-dilation, scoring or sculpting balloon angioplasty, and use of atherectomy (a minimally invasive endovascular surgery technique for removing atherosclerosis from blood vessels within the body.) and protection devices will be performed at the operator's discretion, followed by MV stenting.

The operator will also decide in both groups about the length and size of the implanted stent. Procedural optimization, such as post-dilation or additional stent implantation will be performed based only on the angiographic findings, according to the discretion of the operator.

The Pre and post stenting OCT + FFR for side branch are the research procedures.

OCT pullback will be performed after lesion preparation before stenting (OCT-PRE) and after PCI (OCT-POST). FFR measurement in the side branch will be performed, if the coronary angiogram shows SB DS < 70%, TIMI grade 3 flow and no dissection in the side branch.

To perform FFR measurements, the pressure wire will be passed through the struts of the MV stent into the SB and FFR will be measured at least 5 mm distal to the jailed SB stenosis. Adenosine will be infused through the

Protocol Title:	Optical Coherence Tomography Predictors of Functionally Significant Side Branch Compromise after Provisional Main Vessel Stenting In Bifurcation Lesions Assessed by Fractional Flow Reserve (ORBID – FFR)
Principal Investigator Name/Contact Info:	[name]./ [name]/ [contact]
Primary Contact Name/Contact Info	[name] /[name] / [contact] [name] /[name] [contact]
Date Revised:	January 19, 2017
Study Number:	HSM# 16-00041/ GCO#1: 16-0204(0001)

femoral vein at least 140 µg/kg per minute to induce maximal coronary blood flow.

g) Specimen Banking

Not Applicable

h) Data Management and Confidentiality

Confidentiality of subject medical information will be ensured by providing unique identifiers (Subject ID) for data transmitted from the enrolling centers to St. Jude Medical Center. Designated representatives will not receive identifiable subject information.

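### Side-branch stenosis of exactly 70% satisfies both the entry range and the primary endpoint, so an unchanged side branch can count as compromised

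*Combined protocol and SAP*

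**What the plan says.** Four places in the combined protocol and SAP bear on this.

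- **Inclusion and Exclusion Criteria (5b), angiographic list:** "The target lesion should have SB DS 30 - 70"%. The procedures section (5f) repeats the range: "SB stenosis 30-70% and SB reference diameter > 2mm will be enrolled in the study". Neither place puts a strict inequality at the upper end.
- **Study Endpoints (5e):** SB compromise is SB DS at or above "70%, or dissection or TIMI < 3". The sentence gives no baseline value, no minimum worsening and no time point. That the endpoint is read after main-vessel stenting comes from the Objectives (section 1), where the incidence of SB compromise is the first item.
- **Procedures (5f), FFR rule:** SB FFR is measured "if the coronary angiogram shows SB DS < 70%, TIMI grade 3 flow and no dissection in the side branch".
- **Data analysis and Statistical methods (section 5):** a t-test is the only test named, and it is not attached to any endpoint. The same section plans an offline analysis of acute loss in SB diameter and area, but this is not part of the primary endpoint.

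**The concern.** An incidence should count side branches that become compromised. Under the rules as written, one that starts at 70% and stays there is an event without having changed. The same patient gives no FFR value, and so adds an event to the primary endpoint and nothing to the functional analyses.

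The inclusive reading of the range is the ordinary one, and the plan's own usage supports it. Where 70% is meant to be excluded, the plan uses a strict inequality: for the intermediate main-vessel stenosis category in the same criteria list, and in the FFR rule. Where a change is meant, it says so, as in the secondary endpoint "OCT predictors of SB TIMI flow reduction after main vessel PCI". The primary endpoint does neither. What is at stake is the level of the reported incidence and a clean definition of the primary endpoint.

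**Working it through.** **1. The plan's own figure.** The only sample-size figure is 75 per lipid group for an odds ratio of 2.8 at 25% FFR-positive prevalence and 80% power. I take 25% as the reference-group rate and assume two-sided alpha 0.05, which is not stated.

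- Odds in the other group: 2.8 × 0.25/0.75 = 0.933, so its rate is 0.933/1.933 = 0.483.
- The two-proportion formula gives 67 per group without continuity correction and 75 with it.

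The figure is reproduced. It rests on FFR positivity by lipid group, not on SB compromise, so nothing below alters it.

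**2. The overlap.** The entry range is 30% to 70% inclusive. The DS part of the endpoint runs from 70% upward. They share one value, 70%. Applying the rules to a side branch read at 70% both times:

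- eligible under 5b and 5f: yes
- primary event under 5e: yes
- SB FFR measured under 5f: no, because 70% is not below 70%

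**3. How many patients.** The documents give no distribution of baseline SB DS, so the count rests on assumptions.

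- Continuous readings: essentially none at exactly 70%.
- Whole-percent readings spread evenly over 30, 31, …, 70: 41 values, so s = 1/41 = 2.44%, and 150 × 0.0244 = 3.7, about 4 patients.

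**4. Effect on measured incidence, whole-percent case.** Let p be the event rate in patients who enter below 70%, and q the probability that a patient entering at 70% is counted as an event. Then

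measured rate = s·q + (1 − s)·p, and the rise over p is s·(q − p).

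I assume p from 10% to 30% and q from 0.5 to 1.0.

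| p | measured, q = 0.5 | measured, q = 1.0 | rise (points) |
|---|---|---|---|
| 10% | 11.0% | 12.2% | 1.0 to 2.2 |
| 20% | 20.7% | 22.0% | 0.7 to 2.0 |
| 30% | 30.5% | 31.7% | 0.5 to 1.7 |

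The range is +0.5 to +2.2 points. With continuous readings the rise is about 0.

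**The case against.** The strongest reply is that an absolute post-stent threshold is a legitimate endpoint when entry already restricts the baseline. Entry excludes SB DS above 70%, so by DS an unchanged side branch can be an event only at one value. The plan also measures acute SB loss offline, so such a patient could be recognised later. Most of this stands, and it limits the point to a boundary error. It does not remove the error: no passage excludes 70% at entry, and the acute-loss analysis does not feed into the endpoint.

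A reader might infer more than the documents support:

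- **That the reading method is wholly unspecified.** The criterion sits under the angiographic inclusion heading, eligibility is confirmed after the diagnostic angiogram, and the post-stent FFR rule refers to the coronary angiogram. Angiography is the modality at entry and at the post-stent check. What remains open is visual or quantitative reading.
- **That the comparison of randomised arms is biased.** No passage says that the primary endpoint is compared by arm, or that the t-test applies to it. Random allocation would in any case not place boundary patients systematically in one arm.
- **That many patients are affected.** Even spreads over 5-point or 10-point steps would put 1/9 (about 17 of 150) or 1/5 (30 of 150) at 70%. The documents give no basis for either grid.
- **That the TIMI component has the same overlap.** Entry states "The target vessel must have a Thrombolysis in Myocardial Infarction (TIMI) flow grade 3 at baseline", so the documents do not establish one there.

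**Conclusion.** The point holds as a defect in how the entry range and the primary endpoint fit together. It is worth correcting because it touches the primary endpoint and the first objective, and correction costs almost nothing. Its likely size is small: about 0 to 4 of 150 patients, and 0 to about 2.2 points of incidence, unless SB DS is read in coarse visual steps. These figures rest on the inclusive reading of the range and on assumed values for the spread, p and q. Sample size and the lipid-group power figures do not change.

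**What to change.** 1. Reconcile sections 5b, 5e and 5f so that one reading cannot satisfy both entry and endpoint. Write the entry range as SB DS at least 30% and below 70% in both places where it appears. This matches the strict bound already used for the main-vessel category and the FFR rule.
2. State whether SB DS is read visually or quantitatively on the angiogram, and use the same reading before and after stenting.
3. Name an analysis for the primary endpoint. It is binary, so use logistic regression that includes the baseline SB DS recorded for eligibility, for whichever group or predictor comparison the plan specifies. The strict bound alone still lets a move from 69% to 70% count as an event. The covariate does not reclassify that patient, but it takes the starting value into account.

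The cost is that patients at exactly 70% become ineligible (about 0 to 4 in 150, more if readings are coarse), and the analysis takes slightly more work. Baseline SB DS is already assessed, so no procedure is added, and the planned 150 stays as it is.

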Title: Optical Coherence Tomography Predictors of Functionally Significant Side Branch Compromise after Provisional Main Vessel Stenting in Bifurcation Lesion Assessed by Fractional Flow Reserve (ORBID-FFR)

PI: [name]

NCT03115580

Document Date: January 19, 2017

 Mount Sinai	Protocol Title:	Optical Coherence Tomography Predictors of Functionally Significant Side Branch Compromise after Provisional Main Vessel Stenting In Bifurcation Lesions Assessed by Fractional Flow Reserve (ORBID – FFR)
	Principal Investigator Name/Contact Info:	[name]./ [name]/ [contact]
	Primary Contact Name/Contact Info	[name] /[name] / [contact] [name] /[name] [contact]
	Date Revised:	January 19, 2017
	Study Number:	HSM# 16-00041/ GCO#1: 16-0204(0001)

MSSM Protocol Template HRP-503a

Instructions:

1. Prepare a document with the following sections. Note that, depending on the nature of your research, certain sections below may not be applicable. Indicate N/A as appropriate, explaining where possible.
2. For any items described in the sponsor's protocol, grant application or other source documents submitted with the application, you may reference the title and page numbers of these documents rather than cutting and pasting into this document. **Do NOT refer to any derived documents, such as the Sample Consent document, or other internal documents required with the submission.**
3. If you reference page numbers, attach those pages to this protocol.
4. When you write a protocol, keep an electronic copy. You will need to modify this copy when making changes.

Brief Summary of Research (250-400 words):

Protocol Title: Optical Coherence Tomography Predictors of Functionally Significant Side Branch Compromise after Provisional Main Vessel Stenting in Calcific Coronary Artery Disease (CAD) Assessed by Fractional Flow Reserve (ORBID-FFR)

This is a single-center, randomized study in patients with stable coronary artery disease.

1) Objectives:

Research Question:

To analyze the incidence of SB compromise after provisional main vessel stenting in calcified bifurcation lesions of CAD patients, determine the incidence and OCT predictors of functionally significant SB stenosis defined as FFR ≤ 0.8 and to compare the FFR values with 3D-OCT measurements of jailed SB ostium after MV stenting.

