Figure 2. 3D quantitative coronary angiography (QCA) and cut-plane analysis of side branch ostium from the main branch OCT pullback for bifurcation PCI before (top row) and after (bottom row) stenting.

We assumed FFR (+) prevalence of either 20% or 25% based on previous studies. We also assumed that there would be a roughly equal proportion of patients with high and lipid levels.

Based on these assumptions, we will need at least 75 patients per EACH high lipid and low lipid groups to detect an odds ratio (OR) of 2.8.

Protocol Title:	Optical Coherence Tomography Predictors of Functionally Significant Side Branch Compromise after Provisional Main Vessel Stenting In Bifurcation Lesions Assessed by Fractional Flow Reserve (ORBID – FFR)
Principal Investigator Name/Contact Info:	[name]./ [name]/ [contact]
Primary Contact Name/Contact Info	[name] /[name] / [contact] [name] /[name] [contact]
Date Revised:	January 19, 2017
Study Number:	HSM# 16-00041/ GCO#1: 16-0204(0001)

The table below is showing the detectable OR we might have under different assumptions of the patient population assuming an equal proportion of high/low lipid level groups.

Prevalence of + FFR	Patients per group	Detectable OR with 80% power
0.2	50	3.7
0.2	75	2.9
0.2	100	2.5
0.25	50	3.5
0.25	75	2.8
0.25	100	2.4

a) Recruitment Methods

We will recruit patients referred to the interventional cardiologists involved on this study based on their medical history who require a PCI of the main vessel with drug eluting stent implantation for the treatment of stable CAD where impact on the side branch can be access. Patients will be undergoing a PCI using an angiography and OCT-guided strategy. Patients will be approached in the ambulatory unit before their procedure to obtain consent and review and confirm the inclusion and exclusion criteria of the protocol.

The PI and the research team will identify potential subjects based on their medical history. Potential patients will be approached in the ambulatory unit before their procedure to obtain consent and check the inclusion/exclusion criteria.

In all cases, the Principal Investigator, Sub-Investigator or member of the Research Team will discuss the research trial and informed consent document in full detail following Good Clinical Practices and HIPAA Laws. During the informed consent process, all of the potential subject's questions will be answered. Subjects will be given a copy of the signed

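### The only stated power is for FFR-positive side branches by lipid group, a dichotomised secondary endpoint not listed in that form; the primary endpoint and the randomised comparison have no power statement

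*Combined protocol and SAP*

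**What the plan says.** **Objective.** The research question in 1) Objectives is, among other things, to "determine the incidence and OCT predictors of functionally significant SB stenosis defined as FFR" at or below 0.8. It also asks for the incidence of SB compromise.

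**Endpoints.** In e) Study Endpoints, "The primary endpoint is SB compromise defined as SB DS" of 70% or more, dissection, or TIMI flow below 3. The first secondary endpoint is "SB FFR after main vessel stenting and its correlation with OCT imaging parameters before PCI". No endpoint mentions the 0.8 cut-off, the incidence of FFR positivity or a lipid grouping.

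**Sample size.** Under Data analysis and Statistical methods: "We assumed FFR (+) prevalence of either 20% or 25% based on previous studies", and "we will need at least 75 patients per EACH high lipid and low lipid groups to detect an odds ratio (OR) of 2.8". The table that follows is headed "Detectable OR with 80% power" and is built "assuming an equal proportion of high/low lipid level groups". Neither alpha nor sidedness is given.

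**Analysis.** The same section names a t-test and says that 3D-OCT parameters will be correlated with side branch FFR. It names no method for a binary outcome.

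**Randomisation and FFR measurement.** Section f) Procedures assigns patients 1:1 to RA or cutting balloon/PTCA. It measures side branch FFR only if the angiogram shows diameter stenosis below 70%, TIMI 3 flow and no dissection.

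**Numbers.** Section c) sets 150 patients. Section j) says that patients who discontinue are not replaced.

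**The concern.** Three things that should line up do not: the event that is powered (FFR positive), the event that is primary (SB compromise), and the contrast that is randomised (RA v cutting balloon/PTCA). The lipid groups are observed, not allocated, so 75 per lipid group says nothing about what 75 per randomised arm can detect.

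The powered event and the primary event also cannot be observed in the same patient. Meeting any component of the primary endpoint takes the patient out of FFR measurement. The FFR power therefore cannot stand in for the primary endpoint, and each primary event removes a patient from the analysis that was powered.

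Two things are at stake. The figures of 150 patients and 80% power could be carried into a report as if they supported the primary endpoint or the treatment comparison. And the question in the title would be answered by a binary analysis whose outcome form, groups, denominator and model are not set out where endpoints and methods are defined.

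**Working it through.** **Step 1: reproduce the plan's figure.** Inputs from the sample-size paragraph are an FFR-positive rate of 25%, odds ratio 2.8 and 80% power. Alpha is assumed to be 5% two-sided, because that fits the table. The 25% is taken as the low-lipid rate.

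- Low-lipid odds: 0.25/0.75 = 0.3333. High-lipid odds: 0.3333 × 2.8 = 0.9333. High-lipid rate: 0.9333/1.9333 = 0.4828.
- d = 0.4828 − 0.25 = 0.2328; p̄ = 0.3664.
- Uncorrected n = [1.96√(2p̄(1−p̄)) + 0.8416√(p₁(1−p₁) + p₂(1−p₂))]² / d² = (1.3355 + 0.5565)² / 0.2328² = 66.1, so 67.
- Continuity-corrected n = (66.07/4) × [1 + √(1 + 4/(66.07 × 0.2328))]² = 74.4, so **75 per group**, as stated.

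The corrected formula gives detectable odds ratios of 3.72, 2.94, 2.55, 3.52, 2.79 and 2.43 for the six rows, against the table's 3.7, 2.9, 2.5, 3.5, 2.8 and 2.4. The third row differs only by rounding. The 2.8 in the text belongs to the 25% rows; at 20%, odds ratio 2.8 would need 83 per group.

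The arithmetic would serve any binary event at these rates. Its labels tie it to FFR positivity and lipid group.

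**Step 2: look for the same inputs elsewhere.**

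| Analysis | Assumed rate | Effect | Power |
|---|---|---|---|
| FFR positive, high v low lipid | 20% or 25% | OR 2.4 to 3.7 | 80% |
| SB compromise (primary) | none | none | none |
| RA v cutting balloon/PTCA | none | none | none |

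**Step 3: effect of patients without FFR.** The share is not given, so 10%, 20% and 30% are assumed, spread evenly over the lipid groups with the rates unchanged. With n per group, n′ = n(1 − 1/(nd))² and power = Φ{[d√n′ − 1.3355] / 0.6612}, where 0.6612 = √(p₁(1−p₁) + p₂(1−p₂)).

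| Without FFR | n per group | n′ | Power for OR 2.8 at 25% |
|---|---|---|---|
| 0% | 75 | 66.7 | 80% |
| 10% | 67.5 | 59.2 | 75% |
| 20% | 60 | 51.7 | 70% |
| 30% | 52.5 | 44.3 | 63% |

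**Step 4: what 75 per randomised arm could detect for SB compromise.** The documents give no rate, so control rates are assumed. Same formula, two-sided 5%, 80% power; changes are in percentage points.

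| Assumed control rate | Fall / rise, no correction | Fall / rise, continuity-corrected | Power to detect a halving, uncorrected / corrected |
|---|---|---|---|
| 20% | 15 / 21 | 16 / 22 | 40% / 32% |
| 25% | 17 / 22 | 18 / 23 | 50% / 42% |
| 40% | 21 / 23 | 22 / 24 | 77% / 71% |

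Method matters. A fall from 20% to 5% has power 0.80 uncorrected but 0.72 with the correction that the plan's own table implies.

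**The case against.** The strongest defence is that the powered contrast is not foreign to the plan. FFR at or below 0.8 is a declared objective. Lipid content of the main vessel lesion is presented in 2) Background as an OCT finding from the earlier 30-patient study. If the lipid groups mean OCT plaque lipid, FFR positivity by lipid group is a dichotomised form of the first secondary endpoint. This stands. A reader might infer that FFR at or below 0.8 was never declared, or that FFR is to be used only as a continuous variable; the documents support neither. The endpoint list does not say continuous, and both the objective and the sample-size paragraph treat FFR as binary. What is missing is alignment: the list lacks the binary form and the lipid grouping, and the sample-size text speaks only of lipid levels, with no cut-off.

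It is also fair to say that the sample-size paragraph labels its inputs clearly as FFR and lipid, so a careful reader would not misattribute them. Nor does any section say that SB compromise will be tested by arm; the objective is to analyse its incidence. That weakens any charge that a planned test is underpowered. It does not explain why a study that randomises 1:1 and names a primary endpoint leaves both without a stated precision, power or analytic status.

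Finally, a single detectable range such as 15 to 21 points is tempting. It holds only for an assumed 20% control rate without continuity correction, and the plan's 20% and 25% are FFR-positive rates, not SB compromise rates.

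**Conclusion.** The point holds in limited form. The stated 80% power belongs to a dichotomised secondary endpoint that is an objective but is not listed in that form and has no matching analysis. The primary endpoint and the randomised comparison have no power statement.

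One might conclude that the trial is underpowered for its primary endpoint. The documents cannot show that, because they give no SB compromise rate, target effect or between-arm test. They do show that the 80% cannot be borrowed for it. On the assumed rates above, a null between-arm result could leave large effects unexcluded.

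The 80% is also the most favourable case for the FFR analysis, since it needs FFR in all 150 patients while the protocol withholds it from everyone with a primary event. The 75%, 70% and 63% figures rest on assumed losses, an inferred two-sided 5% alpha and the continuity-corrected method.

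This should be corrected, but it does not prevent the study from proceeding.

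**What to change.** 1. In e) Study Endpoints, list FFR at or below 0.8 after main vessel stenting, by lipid group, as the key secondary endpoint. Define the lipid measure and its cut-off. Report incidence with a 95% CI in a stated denominator, making clear how patients without FFR are counted.
2. In Data analysis and Statistical methods, replace the t-test for this endpoint with a logistic model that gives the odds ratio for lipid group with a 95% CI. State alpha and sidedness.
3. In the sample-size paragraph, say that the 80% power applies to this analysis only. Restate it for the number of patients expected to have FFR, with the assumed share without it.
4. State that the RA v cutting balloon/PTCA comparison of SB compromise is not powered and will be reported as an estimate with a 95% CI. If a detectable difference is quoted, give its assumed control rate and method. For example, at 75 per arm, two-sided 5%, 80% power and no correction: about 15 points down or 21 up from an assumed 20%, and 21 down or 23 up from an assumed 40%.

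The cost is wording, and a stated power that looks less favourable. No extra patients are needed, because the change restates the power for patients with FFR and does not try to restore 80%.
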